## **3.6.8 Other Safety Evaluations**

### **3.6.8.1 Vital Signs**

Vital signs will be assessed at screening, baseline and throughout the study. Descriptive statistics of baseline value, post-baseline value, and change from baseline value for heart rate, blood pressure, temperature, and respiratory rate will be provided for each scheduled time

point with available data in at least 10% of subjects. [Table 3.6.8.1-1](#) presents the summary to be prepared for vital sign parameters.

**Table 3.6.8.1-1 Vital Sign Parameters to be Summarized**

Summary	Population
Change from Baseline in Vital Sign Parameters	As-treated

### 3.6.8.2 Electrocardiogram

Electrocardiogram (ECG) parameters will be assessed at baseline as well as throughout the study. Abnormal ECG parameters (PR, QRS, QTcF) will be summarized using descriptive statistics; changes from baseline to scheduled time of evaluation and to the maximum post-baseline values will be summarized. The QTcF will be considered as the primary correction method to assess subject cardiac safety.

The number and percentage of subjects having the following notable ECG interval values on treatment will be summarized:

- Maximum QTcF intervals > 450 milliseconds, > 480 milliseconds, and > 500 milliseconds.
- Maximum changes from baseline in QTcF > 30, >60, and > 90 milliseconds.

### 3.6.8.3 ECOG Performance Status

Eastern Cooperative Oncology Group (ECOG) performance status will be assessed at baseline as well as throughout the study. ECOG will be summarized by study visit and will include descriptive statistics for the value of the parameters and the changes from baseline.

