### 3 STATISTICAL METHODS

#### 3.1 General Considerations

Tabular summaries will be presented by treatment group. Categorical data will be summarized by frequency distribution (number and percentage of subjects falling within each category). Continuous variables will be summarized by descriptive statistics including N, mean, standard deviation, median, and range (minimum and maximum). All available data will be used and thus missing data will not be imputed. In general, subjects with missing data for a parameter will be excluded from the summary of this parameter. Tables will be supported by data listings showing the original data forming the basis for the summaries. Data listings will be sorted by treatment group, subject number and date collected where applicable.

In general, unless stated otherwise, two-sided confidence intervals will be produced at 95%. Baseline values will be defined as the last valid assessment prior to the first administration of investigational product.

The data analyses will be conducted using the SAS® System (SAS Institute, Inc., Cary, NC, USA) Version 9.3 or above. All analysis outputs will be validated according to MedImmune SAS programming standards and MedImmune validation procedures.

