Baseline Eastern Cooperative Oncology Group (ECOG) performance status will be summarized using frequency distributions for the collected categories.

Smoking history will be summarized.

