### **3.6.7 Clinical Laboratory Evaluation**

Laboratory tests will be grouped according to hematology, serum chemistry, urinalysis, and thyroid function tests (TSH, free thyroxine T4). For all continuous laboratory assessments, absolute value and change from baseline will be summarized for each scheduled assessment, “worst-case” (nadir and/or zenith) on treatment, and the last assessment on-treatment using descriptive statistics. Laboratory abnormalities with toxicity grades according to the NCI CTCAE 4.03 will be derived according to laboratory values. Shift tables from baseline to worst toxicity grade on treatment will be presented. Separate summaries indicating hyper- and hypo- directionality of change will be produced, where appropriate. In addition, the number and percentage of subjects experiencing at least 2-Grade shift, and any shift to a worst post-baseline toxicity Grade of 3 to 4 from baseline will be summarized. For each lab test condition, percentages are calculated based on the number of treated subjects who have a baseline and at least one post-baseline assessment. In the shift table analysis, for a given subject, if a subject has both missing and non-missing CTCAE grades for one laboratory test, the missing CTCAE grade of that laboratory test will be treated as the lowest grade.

Laboratory abnormalities with toxicity grades according to the NCI CTCAE 4.03 will be derived for the following parameters:

Hematology: Anemia (Hemoglobin decreased), White Blood Cell decreased, Neutrophils decreased, Platelets decreased, Lymphocytes decreased

Serum chemistry: Alanine Amino Transferase (ALT) increased, Aspartate Amino Transferase (AST) increased, Alkaline Phosphatase (ALP) increased, Total bilirubin increased, Creatinine increased, Magnesium hypo and hyper, Sodium hypo and hyper, Potassium hypo and hyper, Corrected calcium hypo and hyper, Glucose hypo and hyper, Cholesterol high, GGT increased, Lipase increased, Amylase increased.

For thyroid function tests (TSH, free thyroxine T4) with no CTCAE grading, summary table of shifts from baseline relative to the normal range in thyroid function will be provided. Number of subjects will be summarized for those with normal baseline and at least one post-baseline TSH value below LLN and a concurrent free Thyroxine above the ULN and those with normal baseline and at least one post-baseline TSH value above ULN and a concurrent free Thyroxine below the LLN.

Liver Function Parameters

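### Post-baseline ECOG is summarised only visit by visit among subjects scored at that visit, so no planned table shows how many subjects ever worsened

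*SAP*

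**What the plan says.** Section 3.6.8.3 says that ECOG is assessed at baseline and throughout the study, and then defines the analysis in one sentence: "ECOG will be summarized by study visit and will include descriptive statistics for the value of the parameters and the changes from baseline".

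Section 3.1 supplies the conventions behind that sentence:

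- For continuous data: "Continuous variables will be summarized by descriptive statistics including N, mean, standard deviation, median, and range (minimum and maximum").
- For categorical data: "Categorical data will be summarized by frequency distribution (number and percentage of subjects falling within each category").
- For missing data: "In general, subjects with missing data for a parameter will be excluded from the summary of this parameter". The same section rules out imputation.

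At baseline, section 3.3.2 handles ECOG as categorical: "performance status will be summarized using frequency distributions for the collected categories".

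Other safety measures get a per-subject worst value. For laboratory grades, section 3.6.7 states: "Shift tables from baseline to worst toxicity grade on treatment will be presented". That section also counts subjects with a shift of at least 2 grades, and bases percentages on treated subjects with a baseline and at least one post-baseline value. Creatinine clearance has a shift table to the worst on-treatment category. Section 3.6.8.2 summarises the maximum QTcF and its maximum change against thresholds.

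**The concern.** Two things sit badly together. First, one ordinal scale is handled in two ways: as frequencies at baseline and, on the natural reading of section 3.1, as N, mean, SD, median and range afterwards. A mean ECOG change of, say, 0.1 has no direct clinical reading; the number of subjects who moved from one category to another does.

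Second, the summary is cross-sectional and uses observed scores only. Each visit row describes whoever was scored at that visit. A subject who worsens at one visit and then stops contributes to one row and is absent from the rest. Nothing links the rows, so the number who ever worsened cannot be read from them.

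Safety and tolerability is a primary objective of both parts (section 2.1.1). In an uncontrolled description of this kind, the share of subjects whose performance status declined is the most useful figure that ECOG can supply, and the plan does not produce it.

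**Working it through.** The SAP states no numerical figure for ECOG, so there is none to reproduce. Two illustrations show what the planned table can and cannot reveal. All rates below are assumptions; only the arm size of 46 (Arm A, section 2.4) comes from the SAP.

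**1. No dropout: the rows do not determine the count.** Take 40 subjects, 4 visits and everyone scored at every visit.

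- Data set A: the same 4 subjects are one point worse at all 4 visits.
- Data set B: a different group of 4 subjects is one point worse at each visit, then recovers.

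At every visit, both sets give N = 40, mean change 4/40 = 0.10, SD = √(40 × 0.10 × 0.90 / 39) = 0.304, median 0 and range 0 to 1. Ever worsened: 4 in A, and 4 × 4 = 16 in B. Category frequencies of change at each visit are also identical (4 of 40), so frequencies by visit would not recover the count either.

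**2. Worsening followed by exit: the visit means can stay low.** Assume six visits. In each interval a fraction w of subjects not yet worsened becomes one point worse and is scored once at that visit. A fraction e of these then leaves, those who remain stay one point worse, and a fraction d of all others drops out for other reasons.

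Let U be the share of the starting group still attending and not yet worsened before the visit, and S the share attending who had worsened earlier. Start at U = 1, S = 0.

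- Mean change at the visit = (wU + S) / (U + S)
- Next U = U(1 − w)(1 − d)
- Next S = [S + wU(1 − e)](1 − d)
- Ever worsened = sum of wU over six visits = w(1 − r⁶)/(1 − r), with r = (1 − w)(1 − d)

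*w = 0.08, d = 0.08, everyone who worsens leaves (e = 1).* S stays 0, so the mean is 0.08 at every visit. r = 0.92 × 0.92 = 0.8464. Ever worsened = 0.08 × (1 − 0.8464⁶)/(1 − 0.8464) = 32.9%, about 15 of 46 (46 × 0.329).

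*Same w and d, 80% leave (e = 0.8).* At visit 2, U = 0.8464 and S = 0.08 × 0.2 × 0.92 = 0.0147, giving a mean of (0.0677 + 0.0147)/0.8611 = 0.096. By visit 6, U = 0.4344 and S = 0.0449, giving (0.0348 + 0.0449)/0.4793 = 0.166. The means therefore run from 0.08 to 0.17. Ever worsened does not involve e and is still 32.9%.

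*w = 0.10, d = 0.05, e = 0.8.* r = 0.90 × 0.95 = 0.855. Ever worsened = 0.10 × (1 − 0.855⁶)/0.145 = 42.0%. The means run from 0.10 to 0.21.

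*Contrast: w = 0.08, d = 0.08, nobody leaves because of worsening (e = 0).* At visit 6, U = 0.4344 and S = 0.2247, giving a mean of (0.0348 + 0.2247)/0.6591 = 0.39, with the same 32.9% ever worsened. The low means in the earlier settings therefore come from the assumed exit and are not a general property of the display.

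**The case against.** The strongest reply is that section 3.6.8.3 describes a conventional display and that a shift table is an optional extra. The sentence says what the summary will include, which does not exclude counts, and section 1 leaves table templates to a programming plan that is not shown. The word mean does not appear in section 3.6.8.3; it follows only from section 3.1, which also gives N, median and range. Falling N shows attrition, the maximum shows that someone worsened, and section 3.1 provides listings of the original data. Decline that ends treatment appears in reasons for ending treatment (section 3.3.1), in adverse events leading to discontinuation or death (section 3.6.2), and in PFS and OS. ECOG triggers no decision.

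Much of this stands, and it limits the importance of the point. It does not remove it. The range says that at least one subject worsened, not how many. Listings report individuals without counting them. The disposition, event and survival tables count different things. The programming plan could add a shift table, but this SAP does not require one.

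The exit mechanism is also fairly challenged. The SAP nowhere says that worsening removes a subject from later ECOG scoring, and it does not say whether ECOG is scored at an end-of-treatment visit. A separate row for such a visit would show part of the decline. The second illustration is conditional on this; the first is not.

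**Conclusion.** The point holds as a modest one. The plan names a poor summary for an ordinal scale, departs from its own handling of that scale at baseline, and has no table of how many subjects ever worsened. Identical visit rows can fit 4 or 16 such subjects out of 40. Where worsening leads to exit, visit means of about 0.08 to 0.17 can accompany 33% worsened, or 0.10 to 0.21 with 42%, under the assumed rates.

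Three stronger readings are not supported:

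- A reader might infer that a near-flat mean change is to be expected in this trial. That depends on most subjects who worsen leaving after one score; with no such exit the mean reaches 0.39 in the same model.
- A reader might infer that deterioration would go unseen. Visit N and range, and the disposition, adverse event, PFS and OS summaries, show part of it.
- A reader might extend the criticism to vital signs, because section 3.6.8.1 restricts them to each scheduled time "point with available data in at least 10% of subjects". Vital signs are continuous, so the ordinal argument does not carry over. Each displayed visit has a minimum and maximum, and the 10% rule concerns sparsely attended time points. That would be a separate question, not examined here.

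No primary endpoint, interim rule or sample size is affected.

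**What to change.** In section 3.6.8.3:

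1. Show the by-visit ECOG summary as number and percentage in each category, in line with sections 3.1 and 3.3.2.
2. Add a shift table from baseline to worst post-baseline ECOG, with n (%) of subjects worsening by at least 1 point and by at least 2 points.
3. Use as denominator the as-treated subjects with a baseline and at least one post-baseline score, as section 3.6.7 does for laboratory tests. Report separately the number of as-treated subjects with no post-baseline score. Dividing by all as-treated subjects would silently count unscored subjects as not worsened.

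Item 2 is the essential part, because item 1 alone does not recover the number who ever worsened. The cost is a few lines of SAP text and one additional table, from data already collected.

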### 3.6.9 Subgroup Analyses

No subgroup analyses are planned.

## 3.7 Immunogenicity

Analysis to immunogenicity will be performed by the MedImmune Clinical Pharmacology & DMPK (CPD) group or designee. The details of the analyses and presentation of these data will be included in a separate PK report.

### 3.8 Pharmacokinetics

Pharmacokinetic data analyses will be performed by the MedImmune Global PK-PD group or designee. The details of the analyses and presentation of these data will be included in a separate PK report.

### 3.9 Continuous Monitoring for Interstitial Lung Disease (Arm A only)

The development of ILD-like events was prospectively identified as a potential safety concern from a review of osimertinib in combination with durvalumab. To ensure subject safety, continuous monitoring of ILD events that occur in subjects enrolled in Arm A will be performed. The study team, including the medical monitor, will review all potential cases of pneumonitis/ILD via the automatic notification system from AESI reporting by the investigators from the start of the trial. As these reports are required within 24 hours, this will facilitate a rapid detection of any potential concerns. In addition, the sponsor will programmatically identify any potential cases of pneumonitis/ILD in the clinical database from the reported AE terms. The list of preferred terms used to identify potential cases of pneumonitis/ILD AE is included in [Appendix 7.3](#). The programmatic listings will commence with the enrollment of the sixth subject and then occur on a regular basis every 2 months thereafter.

If either of these methods of detection identify potential ILD cases exceeding the predefined threshold where the posterior probability of a true ILD rate of  $\geq 10\%$  is more than 90%, then an ILD review meeting will occur to adjudicate the cases and determine if any changes to the trial are necessary ([Table 3.6.9-1](#)). In addition, an ad hoc ILD review can be triggered at any time at the request of the study investigators or sponsor based on evolving data.

**Table 3.6.9-1      ILD Monitoring Plan - Continuous Monitoring Based on the Potential Number of ILD Cases**

Number of Potential ILD Cases Observed	Number of Subjects Enrolled	Observed ILD Rate	Posterior Probability of True ILD Rate $\geq 10\%$
2	6 - 8	25.0%	91.1%
3	9- 14	21.4%	91.3%
4	15 - 21	19.0%	90.8%
5	22 - 28	17.9%	91.0%
6	29 - 36	16.7%	90.3%
7	37 - 43	16.3%	90.9%
8	44 - 46	17.4%	94.4%

ILD = interstitial lung disease.

## 4 INTERIM ANALYSIS

The interim analyses will be performed separately for each dose-expansion cohort (Arm A and Arm B) starting at 10 response-evaluable subjects for Arm A and 20 response-evaluable subjects for Arm B (including subjects dosed at the RP2D in Part 1). Enrollment may be paused at the initial interim analysis for each arm to allow full analysis of results. If the No-Go criteria are NOT met, enrollment may continue. After the initial interim analysis, the subsequent interim analyses will be performed after every 5 additional subjects are response-evaluable. If futility decision is made at an interim analysis, the enrollment will be terminated. An efficacy analysis may also be performed at each interim analysis. The results of the efficacy analysis will not impact on the stopping rule but may trigger other planning activities for further development of oleclumab combinations.

Continuous monitoring based on Bayesian predictive probability will be used for the interim analyses (Lee and Liu, 2008). In this study, for dose expansion cohorts Arm A and B, different ORRs were assumed as the target response rates for decision making. CCI

CCI

CCI

CCI

The interim analyses will be based on the Response-evaluable Population as defined in Section 3.2.

CCI

CCI

[figure not shown]

To assess the operating characteristics of this continuous interim monitoring method, overall go or no-go probabilities, average sample sizes to achieve the decisions, and probabilities of making early decisions were calculated based on 10000 simulations and assumed true response rates (CCI [REDACTED]). Decision consistencies (or accordance) between a design using continuously monitoring and a design without interim monitoring were also compared. The results are shown in [Table](#) for Arm A and [Table](#) for Arm B.

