## 3.2 Analysis Populations

**Table 3.2-1 Analysis Populations**

Population	Description
As-treated population	The As-treated population includes subjects who receive any study investigational product. Subjects will be analyzed according to the treatment they actually receive. All analyses will be performed on the As-treated Population unless otherwise specified.
Response-evaluable population	The Response-evaluable population includes subjects from the As-treated Population who have a baseline disease assessment (DA), have the opportunity to be followed for at least 8 weeks at the time of the data cutoff (ie, dosed at least 8 weeks prior to the time of the data cutoff), and either has at least one post-baseline DA and/or discontinued treatment due to death or disease progression.
DLT evaluable population	The DLT evaluable Population includes subjects enrolled in the dose-escalation phase who receive all planned doses of oleclumab and at least 75% of the daily administrations of osimertinib (Arm A) or AZD4635 (Arm B) during the DLT-evaluation period (defined as from the first dose of both investigational products until the planned administration of the third dose of oleclumab; this corresponding to Day 28 post Dose 1 of oleclumab) and complete the safety follow-up through the DLT-evaluation period or experience any DLTs.

The number and percent of subjects in each subject population for evaluation will be summarized.

Unless stated otherwise, subject disposition and baseline characteristics, exposure to each investigational product (IP), safety analyses, and efficacy analyses will be based on as-treated population; DLT-evaluable population will be used for the RP2D evaluation.

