## **3.4 Efficacy Analyses**

### **3.4.1 Primary Efficacy Endpoint(s) and Analyses**

#### **3.4.1.1 Primary Efficacy Endpoint(s) and Analysis**

The primary efficacy endpoint is objective response per RECIST 1.1 by investigator assessment. Objective response rate (ORR) is defined as the proportion of subjects with a best overall response of confirmed CR or confirmed PR that occur prior to the initiation of

subsequent anticancer treatment. The rules for confirmation of CR or PR are the same as described in Section 3.4.2.1. The primary analysis of ORR will be based on the as-treated population in Part 2 (including subjects dosed at the RP2D in Part 1). ORR will be estimated with a 95% CI using the exact binomial distribution. Subjects that have missing best overall response assessments will be considered non-responders, and will therefore be counted in the denominator, but not in the numerator of ORR. In addition, above analysis may also be performed based on the response -evaluable population in Part 2 (including subjects dosed at the RP2D in Part 1).

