#### **3.4.2.1 Best Overall Response**

Best overall response is defined as the best response (in the order of CR, PR, SD, PD, and not evaluable) among all overall responses recorded from the start of treatment with investigational product until objective documentation of PD, or the last evaluable disease assessment in the absence of PD prior to the initiation of subsequent anticancer therapy or end of the study, whichever occurs first. Best overall response (BOR) will be programmatically derived based on all post-baseline disease assessments that occur prior to the initiation of subsequent anticancer treatment. BOR will be summarized with the number and percentage of subjects for the following categories: CR; PR; SD; PD; and non-evaluable (NE). At least 8 weeks [-3 days] from the first dose of investigational product must elapse without a subsequent radiological disease progression in order to assign a best overall response of SD. The definition of 54 days will allow for the protocol-defined disease assessment window of 8 weeks ( $57 \pm 3$  days) for the first post dose disease assessment.

Confirmation of CR and PR is required and must occur no fewer than 4 weeks after initial documentation of CR or PR. If CR is pending confirmation and is designated at an assessment followed by 1 or more NE assessments, and/or PR assessments such that a) the Target Lesion Response is CR and the Non-Target Lesion Response is NE, or b) the Target Lesion Response is PR due solely to an increase in one or more lymph nodes to a size  $\geq 10$  mm and the Non-Target Lesion Response is either CR or NE, CR may be confirmed thereafter. Similarly, if a PR is pending confirmation and is designated at an assessment followed by 1 or more NE and/or SD assessments, PR may be confirmed thereafter.

In general, subjects not classifiable under the RECIST 1.1 response categories due to insufficient data or early death will be classified as non-evaluable for BOR, but will be counted in the denominator of all response rate calculations. This generalization includes if a subject has missing lesion data at baseline. In this scenario, the subject will be classified as non-evaluable for BOR. If a subject is missing lesion data at a disease assessment and yet progressive disease criteria is met despite the missing data, the subject will be classified as PD.

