**Table 3.6.9-2**

CCI [REDACTED]

CCI [REDACTED]

For example, when the true response rate is 0.4 for Arm A, there is a low probability (8%) that a no-go decision will be made using this paradigm throughout the study. There is about 3.8% probability that a decision would be made before the end of the study.

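### Futility looks admit subjects 8 weeks after dosing, before a confirmed response is possible, so the chance of wrongly stopping an active arm exceeds the stated 8% if looks count confirmed responses

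*SAP*

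**What the plan says.** Section 4 starts futility looks at 10 evaluable subjects in Arm A and 20 in Arm B, then repeats them every 5 evaluable subjects. A futility decision ends enrollment. On who is counted: "The interim analyses will be based on the Response-evaluable Population as defined in Section 3.2". Enrollment may be paused at the first look of each arm only.

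Table 3.2-1 requires that subjects "have the opportunity to be followed for at least 8 weeks at the time of the data cutoff", and that each "either has at least one post-baseline DA and/or discontinued treatment due to death or disease progression".

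Section 3.4.1.1 defines ORR as the "proportion of subjects with a best overall response of confirmed CR or confirmed PR". Under Section 3.4.2.1, confirmation "must occur no fewer than 4 weeks after initial documentation of CR or PR", and the first post-dose scan falls at Day 57 ± 3.

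After the second operating-characteristics table, Section 4 says that at a true rate of 0.4 in Arm A "there is a low probability (8%) that a no-go decision will be made using this paradigm throughout the study", with about a 3.8% chance of a decision before the end. Prior, target rates, No-Go criteria, boundaries and simulation tables are redacted.

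**The concern.** The entry rule and the endpoint run on different clocks. A subject who reached week 8 just before the cutoff counts in the denominator, but even a subject who is responding cannot yet have a confirmed response. A subject who stopped for progression or death by then has a settled outcome. The looks therefore lean one way: an active arm appears less active than it is, by an amount that depends on how fast subjects enrolled.

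At stake is the decision to end enrollment in an active arm. The 8% and 3.8% figures are the plan's visible reassurance against that. The visible description of the simulations names assumed true response rates and mentions neither accrual nor a confirmation lag.

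**Working it through.** **Timing.** The first scan is at about week 8 (Section 3.4.2.1). The earliest confirmation is 8 + 4 = week 12. The PFS censoring rule in Section 3.4.2.4 equates two assessments with 16 weeks, which implies scans 16/2 = 8 weeks apart; on scheduled scans, confirmation then falls at 8 + 8 = week 16. Subjects dosed 8 to 12 (or 16) weeks before the cutoff are counted but immature.

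**How many.** If a look occurs when its nth subject reaches week 8, the expected number immature is about 1 + rate × lag/4.345, with rate per month and lag in weeks. At 2/month this is 1 + 2 × 4/4.345 = 2.8, or 1 + 2 × 8/4.345 = 4.7.

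**The stated figure.** It cannot be derived from the visible inputs, so a predictive-probability design was fitted to it:
- N = 40, Beta(0.5, 0.5) prior, target 0.20, posterior cut 0.90, predictive cut 0.02.
- Stop at ≤0/10, 1/15, 2/20, 4/25, 6/30 or 8/35; final no-go at ≤11/40.
- Early no-go is the sum over looks of P(first at or below the boundary at that look). Total adds P(never stopped and ≤11 of 40).
- Exact binomial recursion at 0.4 gives 3.7% early and 8.0% total, against the plan's 3.8% and 8%. With no looks, P(X ≤ 11 | 40, 0.4) = 7.1%.

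The fit is not unique. Using ≤3/20 gives 4.2% and 8.3%; a design with N = 37 and final no-go at ≤10 gives 3.7% and 7.9%.

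**One look by hand.** At n = 10 the assumed rule stops on zero responses: 0.6^10 = 0.6%. With 3 of the 10 immature it is 0.6^7 = 2.8%; with 5 immature, 0.6^5 = 7.8%.

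**All looks, true ORR 0.4.** Simulation with the first boundary set, Poisson accrual, all responders first responding at week 8, confirmed responses only at looks and full data at the end. Rounded over repeated runs:

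| Accrual per month | Mean immature (wk 12 / wk 16) | Total no-go, confirmed wk 12 | Total no-go, confirmed wk 16 |
|---|---|---|---|
| 0.5 | 1.5 / 1.9 | 9–10% | 10–11% |
| 1 | 1.9 / 2.8 | 10–11% | 13% |
| 2 | 2.8 / 4.7 | 13–14% | 24–25% |
| 4 | 4.7 / 8.4 | 25–26% | 68% |

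The boundary set with ≤3/20 adds up to about 3 points. The early part, which the looks control, rises from 3.7% to about 6–8% at 0.5/month and 11–23% at 2/month.

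**Mitigations in the plan.** If the first look waits until its responses are mature, total no-go is about 12–19% at 2/month and 18–47% at 4/month. If instead 6 Part 1 subjects are already mature (an assumed number), it is about 13–20% and 19–41%.

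**The case against.** The strongest reply is that no visible sentence says the looks count confirmed responses. The ORR definition sits with the primary analysis, on the as-treated population. Section 4 uses another population and its own rule, with redacted blocks on both sides of the quoted sentence. That stands as a limit on confidence. It does not remove the conflict: Section 4 expresses its targets as ORRs, the plan defines ORR once, as confirmed, and no interim exception is visible.

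Four stronger readings are tempting, and the document does not support them.
- A reader might infer that the wrong-stop risk far exceeds 8%. No accrual rate is given, and at 0.5–1/month the reconstructed excess is only about 1 to 5 points. The 68% needs 4/month, confirmation only at week 16, no pause and no mature Part 1 subjects.
- A reader might infer that everyone at a look has only 8 weeks of follow-up. Eight weeks is a minimum; at up to 2/month, about 1.5 to 5 subjects per look are immature.
- A reader might infer that the sponsor's simulations ignored the lag. A no-lag model reproducing 8% and 3.8% does not prove it, since the inputs are hidden. Reading the 3.8% as no-go decisions is itself an assumption.
- A reader might infer that crossing a boundary stops the arm automatically. The text ends enrollment when a futility decision is made, which may leave room for judgment.

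The pause and the Part 1 subjects do reduce the problem. The pause is optional, however, and covers only the first look.

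**Conclusion.** The mismatch is in the visible text, and its direction is certain if looks count confirmed responses: the no-go probability for Arm A at ORR 0.4 is then above that of the same rule with mature responses. The size is not known. The reconstruction runs from about 9–11% at 0.5/month to 25–68% at 4/month, and it rests on fitted boundaries, assumed accrual and, for the upper ends, a scan spacing inferred from the PFS rule.

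The 8% covers the whole study including the final analysis; only the early component is exposed to immature data. No corresponding figure is visible for Arm B, so nothing is quantified there, although the same population rule applies. The definition of the final ORR analysis is not affected. This is a rule that gives a biased result if followed as written, and it is cheap to correct before the first look.

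**What to change.** In Section 4, choose one of two rules.

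1. At a look, a responder is any subject with a documented CR or PR, confirmed or still pending; one that fails confirmation reverts to non-response. Confirmed ORR stays for the final analysis.
2. Only subjects followed long enough for a confirmatory scan, plus its window, are counted at a look.

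Then re-run the simulations with the confirmation lag and a stated accrual assumption, and restate the no-go and early-decision probabilities for both arms. If the redacted criteria already settle the point, one visible sentence in Section 4 saying so is enough, together with a statement that the simulations allowed for the lag.

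**Cost.** Both need SAP wording and a re-run of existing simulations. Option 1 delays nothing and brings total no-go at 0.4 to about 7–10% in the reconstruction. Its price is fewer early stops for an inactive arm. At ORR 0.2 the reconstructed design with mature responses stops early in 77% of trials. If a further 5% of subjects (assumed) show a response that is never confirmed, and it is never withdrawn from the count, early stopping falls to 50–59%; exact recursion at 0.20 + 0.05 = 0.25 gives 51%. Simulating the same 5% with reversion, at 0.5–4/month and with 80–100% of responses first seen at week 8, keeps it at about 71–80%. The reversion clause should therefore be written in. Option 2 avoids that trade-off but delays each look by about 4–8 weeks (12 − 8 or 16 − 8), during which enrollment may continue.
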